11.0 STUDY MANAGEMENT

11.1 Institutional Review Board (IRB) Approval and Consent

It is expected that the IRB will have the proper representation and function in accordance with

federally mandated regulations. The IRB should approve the consent form and protocol.

In obtaining and documenting informed consent, the investigator should comply with the applicable regulatory requirement(s), and should adhere to Good Clinical Practice (GCP) and to ethical principles that have their origin in the Declaration of Helsinki.

Before recruitment and enrollment onto this study, the patient will be given a full explanation of the study and will be given the opportunity to review the consent form. Each consent form must include all the relevant elements currently required by the FDA Regulations and local or state regulations. Once this essential information has been provided to the patient and the investigator is assured that the patient understands the implications of participating in the study, the patient will be asked to give consent to participate in the study by signing an IRB-approved consent form.

Prior to a patient's participation in the trial, the written informed consent form should be signed and personally dated by the patient and by the person who conducted the informed consent discussion.

11.2 Required Documentation

Before the study can be initiated at any site, the following documentation must be placed on file (as applicable).

- A copy of the official IRB approval letter for the protocol and informed consent
- IRB membership list
- CVs and medical licensure for the principal investigator and any sub-investigators who will be involved in the study.
- Investigator's signature documenting understanding of the protocol and providing commitment that this trial will be conducted according to all stipulations of the protocol

11.3 Registration Procedures

All subjects must be registered with the Lineberger Comprehensive Cancer Center. After initial consultation with [name] ([contact], [name]), the subjects will be registered and entered into the web based clinical research platform, Oncore®.

11.4 Data Management and Monitoring/Auditing

All study data will be collected, managed, and stored via PRO Core Survey System using a unique patient identifier. PRO Core is a secure platform for collecting data via web-enabled devices. It facilitates study management through patient tracking reports and email reminders to project staff. It allows symptoms to be tracked from baseline up to 24 weeks post discharge. Data are stored in a secure database managed by the Information Technology Science (ITS) Research Computing group at UNC.

As an investigator-initiated study, this trial may be audited by the Lineberger Cancer Center audit committee.

11.5 Adherence to the Protocol

Except for an emergency situation in which proper care for the protection, safety, and well-being of the study patient requires alternative treatment, the study shall be conducted exactly as described in the approved protocol.

11.5.1 Emergency Modifications

UNC and Affiliate investigators may implement a deviation from, or a change of, the protocol to eliminate an immediate hazard(s) to trial subjects without prior UNC or their respective institution's IRB/IEC approval/favorable opinion.

For any such emergency modification implemented, a UNC IRB modification form must be completed by UNC Research Personnel within five (5) business days of making the change.

11.5.2 Single Patient/Subject Exceptions

Any request to enroll a single subject who does not meet all the eligibility criteria of this study requires the approval of the UNC Principal Investigator and the UNC IRB.

11.5.3 Other Protocol Deviations/Violations

According to UNC's IRB, a protocol deviation is any unplanned variance from an IRB approved protocol that:

- Is generally noted or recognized after it occurs
- Has no substantive effect on the risks to research participants
- Has no substantive effect on the scientific integrity of the research plan or the value of the data collected
- Did not result from willful or knowing misconduct on the part of the investigator(s).

An unplanned protocol variance is considered a violation if the variance meets any of the following criteria:

- Has harmed or increased the risk of harm to one or more research participants.
- Has damaged the scientific integrity of the data collected for the study.
- Results from willful or knowing misconduct on the part of the investigator(s).
- Demonstrates serious or continuing noncompliance with federal regulations, State laws, or University policies.

If a deviation or violation occurs, please follow the guidelines below:

Protocol Deviations: UNC personnel will record the deviation in OnCore®, and report to any sponsor or data and safety monitoring committee in accordance with their policies. Deviations should be summarized and reported to the IRB at the time of continuing review.

Protocol Violations: Violations should be reported by UNC personnel within one (1) week of the investigator becoming aware of the event using the same IRB online mechanism used to report Unanticipated Problems.

Unanticipated Problems:

Any events that meet the criteria for “Unanticipated Problems” as defined by UNC’s IRB must be reported by the Study Coordinator using the IRB’s web-based reporting system.

11.6 Amendments to the Protocol

Should amendments to the protocol be required, the amendments will be originated and documented by the Principal Investigator at UNC. It should also be noted that when an amendment to the protocol substantially alters the study design or the potential risk to the patient, a revised consent form might be required.

The written amendment, and if required the amended consent form, must be sent to UNC’s IRB for approval prior to implementation.

11.7 Record Retention

Study documentation includes all eCRFs, data correction forms or queries, source documents, Sponsor-Investigator correspondence, monitoring logs/letters, and regulatory documents (e.g., protocol and amendments, IRB correspondence and approval, signed patient consent forms).

Source documents include all recordings of observations or notations of clinical activities and all reports and records necessary for the evaluation and reconstruction of the clinical research study.

Government agency regulations and directives require that all study documentation pertaining to the conduct of a clinical trial must be retained by the study investigator. In the case of a study with a drug seeking regulatory approval and marketing, these documents shall be retained for at least two years after the last approval of marketing application in an International Conference on Harmonization (ICH) region. In all other cases, study documents should be kept on file until three years after the completion and final study report of this investigational study.

11.8 Obligations of Investigators

The Principal Investigator is responsible for the conduct of the clinical trial at the site in accordance with Title 21 of the Code of Federal Regulations and/or the Declaration of Helsinki. The Principal Investigator is responsible for personally overseeing the treatment of all study patients. The Principal Investigator must assure that all study site personnel, including sub-investigators and other study staff members, adhere to the study protocol and all FDA/GCP/NCI regulations and guidelines regarding clinical trials both during and after study completion.

The Principal Investigator will be responsible for assuring that all the required data will be collected and entered into the eCRFs. Periodically, monitoring visits will be conducted and the Principal Investigator will provide access to his/her original records to permit verification of proper entry of data. At the completion of the study, all eCRFs will be reviewed by the Principal Investigator and will require his/her final signature to verify the accuracy of the data.

13.0 APPENDICES

13.1 Appendix I – Interview Guide

- 13.1.1 For patient (control group)
- 13.1.2 For caregiver (control group)
- 13.1.3 For patient (intervention group)
- 13.1.4 For caregiver (intervention group)

13.1.1 For patient (control group)

Greeting

Thank you for being here today. We really appreciate you taking the time to participate in this discussion. My name is _____ and will lead the discussion today.

Role

My role today will be to ask some specific questions and to keep the conversation going. We have a lot to cover, so I may need to change the subject or move ahead with the discussion. However, please stop me if you want to add anything or if you have any questions. The interview today will last about 20-30 minutes.

Purpose

The main thing we are interested in today is hearing from you, the expert. We want to hear your experiences about being diagnosed with acute leukemia and the initiation of chemotherapy. Your experiences will help us gain valuable insight on challenges that patients with AML face during chemotherapy. This information will guide us to further develop interventions to manage these challenges in the acute leukemia population.

I would like to state that our conversation is being audiotaped to help us remember what is said. You may ask me to turn off the recorder at any time or simply say you do not want to answer a question. Everything said here today will be confidential. Nothing you say will be connected with your name.

Any questions before we begin?

This section will be conducted at discharge assessment of cycle 1 and cycle 2.

1. How would you describe your mobility before your diagnosis?
2. How would you describe your mobility before your diagnosis now?
3. What do you think will help you continue to stay active?
4. How would you describe your (physical/psychological) symptoms?
5. What has your experience been while being home?

Closing (5 minutes)

Is there anything else we have not yet discussed that you would like to mention related to what we've been talking about?

13.1.2 For caregiver (control group)

Greeting

Thank you for being here today. We really appreciate you taking the time to participate in this discussion. My name is _____ and will lead the discussion today.

Role

My role today will be to ask some specific questions and to keep the conversation going. We have a lot to cover, so I may need to change the subject or move ahead with the discussion. However, please stop me if you want to add anything or if you have any questions. The interview today will last about 20-30 minutes.

Purpose

The main thing we are interested in today is hearing from you, the experts. We want to hear your experiences about noticing [patient's name] cognitive changes after being diagnosed with acute leukemia and receiving chemotherapy. These changes may include difficulties thinking and processing, concentrating, memorizing or any changes you notice may be related. Your experiences will help us gain valuable insight on challenges that patients with AL and caregivers face during chemotherapy. This information will guide us to have an in-depth understanding of cognitive impairment and to further develop intervention to manage these challenges in acute leukemia population and caregivers.

I would like to state that our conversation is being audiotaped to help us remember what is said. You may ask me to turn off the recorder at any time or simply say you do not want to answer a question. Everything said here today will be confidential. Nothing you say will be connected with your name.

Any questions before we begin?

This section will be conducted at discharge assessment of cycle 1 and cycle 2.

1. What would you have wished you had known about [patient's name] acute leukemia?
2. What else might we have done to be helpful to you during the [hospitalization/clinic visit]?

Closing (5 minutes)

Is there anything else we have not yet discussed that you would like to mention related to what we've been talking about?

13.1.3 For patient (Intervention group)

Greeting

Thank you for being here today. We really appreciate you taking the time to participate in this discussion. My name is _____ and will lead the discussion today.

Role

My role today will be to ask some specific questions and to keep the conversation going. We have a lot to cover, so I may need to change the subject or move ahead with the discussion. However, please stop me if you want to add anything or if you have any questions. The interview today will last about 20-30 minutes.

Purpose

The main thing we are interested in today is hearing from you, the experts. We want to hear your experiences about noticing [patient's name] cognitive changes after being diagnosed with Acute Leukemia and receiving chemotherapy. These changes may include difficulties thinking and processing, concentrating, memorizing or any changes you notice may be related. Your experiences will help us gain valuable insight on challenges that patients with acute leukemia and caregivers face during chemotherapy. This information will guide us to have an in-depth understanding of cognitive impairment and to further develop interventions to manage these challenges in the acute leukemia population and with their caregivers.

I would like to state that our conversation is being audiotaped to help us remember what is said. You may ask me to turn off the recorder at any time or simply say you do not want to answer a question. Everything said here today will be confidential. Nothing you say will be connected with your name.

Any questions before we begin?

Intervention Feedback (15-20 minutes)

This section will be conducted during cycles 1 and 2 (days 6 or 7). We will ask questions within 30 days of cycle 3.

1. How would you describe your mobility before your diagnosis and now?
2. What was it like for you to have your RN talk with you daily about your symptoms?
3. What was it like for you to have your OT and PT visit with you during your hospital stay?
4. Describe your experience in the joint meetings to help you develop your SMART goals.
5. What do you think will help you continue to stay active?
6. What did you find the most beneficial about working with your study team during your hospital stay?
7. Do you have general suggestions for improvement of the intervention?

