1.0 BACKGROUND AND RATIONALE

1.1 Study Synopsis

This single institution feasibility and acceptability of study methods are to examine change in pre and post measures of symptoms, function, and QOL comparing 10 control and 10 intervention patients with acute myeloid leukemia (AML). AML is the most common type of acute leukemia. This study is designed to examine a novel palliative and collaborative care intervention in which registered nurses (RNs), occupational therapists (OTs) and physical therapists (PTs) address the physical activity needs of older adults (≥ 60 years) with AML during cycles 1 and 2 (approximately 60 days) of a Palliative and Collaborative Care in Tervention (PACT) (intervention arm only). The eligible population will include patients at the North Carolina Cancer Hospital (NCCH) with a diagnosis of AML, age ≥ 60 years, and receive hypomethylating agents (HMA) or low-dose cytarabine + Venetoclax.

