
 Days 1-7 & 31-37 daily: [name] and patient; 2x a week, RN, OT, PT and patient Days 8-30 & 38-60: RN will call patient 2x/week 	
 Discuss with patient and review knowledge about collaborative work plans.¹⁴ Shift perspective to understand patient's view of progress.¹⁵ Review existing care guidelines for symptoms and function Review outcome and behavioral goals using the elements of collaborative work described previously.^{16,17}

 Days 1-7 & 31-37: RN Monitors symptoms & function daily; 2x week for PT and OT Days 8-30 & 38-60: RN will call patient 2x/week 	
 Assess and monitor 19 symptoms using PRO-CTCAE. Discuss results with patient to increase patient's knowledge about interrelatedness of symptoms.¹⁴ Discuss patient's experience of the symptom Discuss oral medications and adherence with patients

 Days 1-7 & 31-37: Assess adaptive challenges Days 8-30 & 38-60: RN will call patient 2x/week 	
 Plan coping responses to identify challenges associated with symptoms that impede engagement in self-management and function and ways to overcome them.¹⁸ Engage in collaborative work with patient (and PT/OT when appropriate) to shift perspective of staff beliefs about what challenges mean to the patient.¹⁵

 Days 1-7 & 31-37: Exchange information (daily: RN and patient; 2x a week: RN, OT, PT and patient) Days 8-30 & 38-60: RN will call patient 2x/week 	
 Elicit patient's understanding of the symptoms and adaptive challenges and how these interfere with his/her ADLs. RN leads discussion to verify that he/she understands the patients' perspective and to increase patient knowledge about symptoms and function¹⁴. RN, OT and PT probe the patient to elaborate on what they have learned during their discussion.¹⁹

 Days 1-7 & 31-37 Shared understanding (daily: RN and patient; 2x a week: RN, OT, PT and patient) Days 8-30 & 38-60: RN will call patient 2x/week 	
 RN leads the patient and team to synthesize the various perspectives to develop shared understanding of challenge(s), confirming the meaning for the patient. This discussion may lead to shift in each other's perspectives to establish a shared basis for the plan of work.¹⁵

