3.0 STUDY OBJECTIVES/ENDPOINTS

3.1 Primary Objective

Determine feasibility and acceptability of study methods and examine changes in pre- and post-treatment measures of function, patients' self-report of symptoms and QOL, and patients and caregivers' post self-report of readiness for discharge. We will include 10 control and 10 intervention patients.

Feasibility: We plan enrollment of 60% of those approached; achieve 75% retention rate, 75% of intended data collection; and no intervention-related adverse events. The PACT intervention team will have a reduced workload; we will record effort required to deliver the PACT intervention. These feasibility data will inform if, or to what extent, workload is affected to plan future studies and implementation. The team will receive 32 hours of training in palliative care and adaptive leadership approaches. Adherence will be monitored by electronic tracking from OT and PT notes and by self-report.

Acceptability: Assessed by interviews and surveys with patients and their caregivers about their experiences.

Changes in pre-and-post QOL, symptoms, and function: Compare changes between control and intervention.

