8.0 TIME AND EVENTS TABLE

Table 5. Measures

Variable Measured	Measure Description and Reliability	Baseline cycles 1 & 2 (7 days prior or within 3 days of infusion initiation)	Symptom and QOL BOTH GROUPS (About days 1-60)	HMA or low-dose cytarabine completion at cycle 1 & 2 (within 2 days or up to 7 days after the end of infusion)	Post-discharge, 2x week assessments Monday & Thursday INTERVENTION ONLY days 8-30	Before cycle 4 (About day 90)	Data Collector
Demographic and clinical variables	Age, sex, race/ethnicity, insurance, education, income, employment status, marital/partner status, number of people in the household. Treatment type, comorbidities, remission status, blood test results, height and weight.	X			Continuously monitor clinical characteristic, ex: blood result, remission status		Research Assistant
Health Care Utilization	Number and reasons for: emergency department visits, rehospitalizations Length of hospital			Electronic chart abstraction and self-report			Research Assistant
Quality of Life							
QOL	EORTC QLQ-C30 ³⁰ , $\alpha = .89$ (5 functional scales, global health status/QOL scale, cognition, financial impact)	X	X (baseline of cycle 3)			X	Research Assistant
Symptoms							
AML symptoms	PRO-CTCAE 19 items ⁴² (diarrhea, chills, heartburn, nausea, appetite, mouth sores, vomiting, constipation, cough, rash, shortness of breath, fatigue, anxiety, sadness*, nothing will cheer me up, pain, insomnia, concentration, and memory)	X	X	X	X	X	PACT RN
Disease burden	FACT-Leu Additional Concern subscale	X				X	Research Assistant
Function							
Participation in Meaningful Activity	Possibilities for Activity Scale (PActS) ³⁴ - 12 items stratified $\alpha = .77$ – internal consistency .91 - .89	X				X	Research Assistant
Performance Status	Clinician reported Karnofsky Performance Scale ³⁷ - 1 item for clinician; $r = .89$	X		X		X	Research Assistant
Self-care	PASS- Performance Rate Assessment of Self-Care Skills	X					PACT OT
Grip Strength	Hand grip strength	X					PACT OT
Balance	Berg balance test	X					PACT PT
Mobility	Timed Up and Go (3 meter)	X					PACT PT
Function	Activity Measure for Post-Acute Care (AM-PAC) "6 clicks" - 6 items for OT; 6 items for PT; $\alpha = .92 - .94$	X					PACT OT and PT
Cognition abilities	Clock Drawing Assessment	X					PACT OT
Readiness for Discharge and Self-Management							
Readiness for Discharge	Care Transitions Measure ⁴³ , 15 items, $\alpha = .93$			X			PACT RN

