10.0 STATISTICAL CONSIDERATIONS

10.1 Study Design

This is a pilot clinical trial of the PACT intervention in older adults with AML. The primary objective is to assess the feasibility (recruitment and retention) and acceptability of PACT intervention and examine change in pre and post measures of symptoms, function, and QOL comparing 10 control and 10 intervention patients with AML.

Qualitative research does not necessarily predict what might occur, but helps to understand in depth the characteristics of the situation and the meaning brought by participants and what is happening to them at that moment.

Interviews will be semi-structured, face to face with follow-up questions and probes to facilitate a deeper understanding of the patient, caregiver perceptions of the intervention. Interviews will take place on 4 oncology in patient's hospital room or private clinic room and will not last longer than one hour. An interview guide, developed in advance of data collection, will be used to provide a structure to the process (Appendix 13.1).

The interview prompts will focus on the overall perception of the PACT intervention. Each interview will be digitally audio-recorded. Brief field notes will be made before, during (in a non-discrete manner) and after the interviews to make note of points thought to be relevant at the time.

Pseudonyms will be used to protect the identity of the participants. The pseudonym will be linked to demographic and clinical information in a master log. The master log of study participants' names and study codes will be kept in a secure file cabinet in the investigator's locked office.

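### The interview guide for intervention patients (13.1.3) states a caregiver's purpose about cognitive change and has no specific question on the nurse calls at home

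*Combined protocol and SAP*

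**What the plan says.** Section 3.1 makes acceptability part of the primary objective: "Assessed by interviews and surveys with patients and their caregivers about their experiences". Section 10.1 states the intended content of the interviews: "The interview prompts will focus on the overall perception of the PACT intervention". It also describes them as semi-structured, with follow-up questions and probes.

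Table 1 (Section 1.5) divides PACT into two kinds of period. For the treatment weeks it gives "Days 1-7 & 31-37: RN Monitors symptoms & function daily; 2x week for PT and OT". For the weeks between it gives "Days 8-30 & 38-60: RN will call patient 2x/week".

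Section 13.1.3 is the guide for patients who receive PACT. Its purpose paragraph begins "We want to hear your experiences about noticing" and continues with the patient's name in the third person and cognitive changes after diagnosis and chemotherapy. Seven questions follow under an intervention-feedback heading. Question 6 is "What did you find the most beneficial about working with your study team during your hospital stay".

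**The concern.** There are two faults in one script. First, the interviewer tells the patient that the interest lies in noticing cognitive changes in a person who is the patient. PACT is not mentioned in that paragraph. The interview therefore opens on a topic other than the one Section 10.1 sets.

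Second, no scripted question names the calls or the time at home. Control patients are asked about being home (13.1.1, question 5); the patients who receive the calls are not.

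The analysis of acceptability in Section 10.3 uses interview transcripts only, and Section 13.2 lists no acceptability survey. With 10 intervention patients planned, views on a main component of PACT would depend on who happens to raise it and which interviewer happens to probe. That weakens what the pilot can report about the part of PACT delivered outside the hospital or clinic.

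**Working it through.** **Inputs.** Section 1.1 gives a duration of about 60 days over cycles 1 and 2. Table 1 gives days 1-7 and 31-37 (daily nurse contact, team contact twice a week) and days 8-30 and 38-60 (two nurse calls a week). Table 5 has a column headed "Post-discharge, 2x week assessments Monday & Thursday INTERVENTION ONLY days 8-30".

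**Reproducing the duration.** Treatment weeks: 7 + 7 = 14 days. Home periods: 23 + 23 = 46 days. 14 + 46 = 60, which matches Section 1.1.

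**Size of the home component under Table 1.**
- Calendar share: 46/60 = 77%.
- Calls: 2 × 46/7 = 13.1, about 13.
- Share of nurse contacts: 13.1/(13.1 + 14) = 48%.
- Share after adding 4 joint meetings (assumed 2 per treatment week): 13.1/(13.1 + 14 + 4) = 42%. OT or PT visits held apart from the joint meetings would lower it further.

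**Under Table 5 (days 8-30 only).**
- Days: 23. That is 23/60 = 38% of the full period, or 23/(7 + 23 + 7) = 62% of days with scheduled contact.
- Calls: 2 × 23/7 = 6.6, about 7.

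**Purpose paragraphs side by side.** A word-sequence comparison of the four substantive sentences in 13.1.2 (control caregiver) and 13.1.3 (intervention patient) gives a match of 0.95. The differences are minor, such as an abbreviation spelled out and a plural. The intervention-caregiver script (13.1.4) does open by asking for feedback on the intervention, but it also keeps a clause on cognitive change.

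**Questions in 13.1.3 against the parts of PACT.**

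| Part of PACT | Question |
|---|---|
| Daily nurse talks (treatment weeks) | 2 |
| OT and PT visits | 3, limited to the hospital stay |
| Joint meetings and goals | 4 |
| Benefit of the study team | 6, limited to the hospital stay |
| Nurse calls at home | none |
| Intervention as a whole | 7, suggestions for improvement |

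Questions 1 and 5 concern mobility and staying active.

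**Timing.** Section 13.1.3 places interviews on day 6 or 7 of cycles 1 and 2, and again within 30 days of cycle 3. The cycle 1 interview precedes every home call. The cycle 2 interview (study day 36 or 37) follows the first home period only. Table 5 marks the interview only at the end of the cycle 1 and 2 infusions and shows none for cycle 3.

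**The case against.** A reader might infer that acceptability is not elicited at all for three quarters of PACT, and that the trial could say nothing about the home part. The documents do not support that. Question 7 has no hospital limit. Probes are allowed, and a semi-structured guide need not list every component. Intervention caregivers are asked what was most and least helpful about the intervention as a whole (13.1.4), and a willing caregiver is an inclusion criterion. Under 13.1.3, the cycle 2 interview and the one around cycle 3 come after patients have begun to receive calls. All of this stands.

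The 77% also counts calendar days, not content. The denser contacts fall in the treatment weeks, and the figure depends on Table 1 alone.

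It can also be said that Section 10.1 speaks of prompts, not introductions. Five of the seven questions (2, 3, 4, 6 and 7) concern PACT and none concerns cognition. That is fair: the wrong introduction is not shown to bias the answers, and that it was copied from the caregiver script is an inference from the wording and the placeholder. It is still the text the interviewer would read to the patient, and it misstates both the subject and the person.

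Finally, the feasibility rule in Section 10.2 rests on recruitment and retention, so no error rate or decision threshold is affected. That stands too.

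**Conclusion.** The point holds as a gap in the interview instrument. The purpose paragraph in 13.1.3 is wrong for its audience and does not mention PACT, and the nurse calls at home are not specifically asked about. Acceptability of the home component would be captured unevenly; the documents do not show that it would be absent.

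Under Table 1 the calls span 46 of 60 days, about 13 calls and roughly 42-48% of scheduled contacts. The range depends on whether the assumed 4 joint meetings are counted. Under Table 5 the period is 23 days and about 7 calls, and the gap in the guide remains. The conclusion about other sources rests on the text that can be read, since Section 3.5 is redacted.

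The change is worth making because the interviews are the only acceptability data that Section 10.3 analyses, and it is cheap.

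**What to change.** 1. Replace the purpose paragraph in 13.1.3 with wording addressed to the patient that asks for feedback on PACT. The intervention-feedback clause of 13.1.4 can serve as the model, without its cognitive-change text; copying 13.1.4 unedited would carry that text over.
2. In question 6, widen the limit from the hospital stay to the whole study. This also suits patients treated in clinic.
3. Add one question for the cycle 2 and cycle 3 interviews, for example: *How did you find the nurse's phone calls at home: their number, their timing and their usefulness to you?* It has no place in the cycle 1 interview, which comes before any call.
4. Reconcile Table 1 with Table 5 on the days of post-discharge contact, and 13.1.3 with Table 5 on whether there is an interview around cycle 3.

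The cost is a script edit with an IRB submission and about two more minutes in an interview planned for 20-30. The change is best made before the intervention-arm interviews start, which under Section 2.0 is after the controls have finished. If some have already been held, the audit trail in Section 10.3 should record which version of the guide each patient received.
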